9.7.1.7 Pharmacokinetic, Pharmacodynamic, and Pharmacogenomic/Pharmacogenetic Analyses

PHARMACOKINETIC ANALYSES

The Safety Analysis Set will be used for individual BAN2401 serum and CSF concentration listings. The PK Analysis Set will be used for summaries of BAN2401 serum and CSF concentrations.

A population PK approach will be used to characterize the PK of BAN2401. The effect of covariates (ie, demographics) on BAN2401 PK will be evaluated. The PK model will be parameterized for clearance (CL) and volumes of distribution. Derived exposure parameters such as AUC will be calculated from the model using the individual posterior estimate of CL and dosing history.

PHARMACODYNAMIC ANALYSES

The PD Analysis Set will be used for the summaries and analyses of CSF biomarkers. CSF A β (1-42), t-tau, and p-tau will be assessed and data presented graphically. Baseline levels and changes in t-tau and p-tau will be correlated with changes in CSF A β (1-42), imaging markers, and *APOE4* status. Summary statistics for CSF biomarkers will be assessed for evidence of a dose relationship.

PHARMACOKINETIC-PHARMACODYNAMIC ANALYSES

The PK/PD relationship between CSF biomarker levels and serum PK parameters or CSF concentrations of BAN2401 will be explored graphically and any emergent relationship will be explored through population PK/PD modeling. These serum PK parameters include SS, C_{max} and AUC_(0-t) derived from the population PK model. The PK/PD relationship between serum PK parameters and CSF concentrations of BAN2401 with other biomarkers may also be explored using similar methods.

Additionally, the relationship between various serum PK parameters (eg, C_{max}) or CSF concentrations of BAN2401 (Core Study only) and the ADCOMS at 12, 18, 30, and 42 months, and the relationship between various serum PK exposure parameters or CSF concentrations of BAN2401 and the change from Baseline for 12, 18, 30, and 42 months in the ADAS-Cog, the CDR-SB, and the MMSE, will be explored graphically (revised per Amendments 08 and 11). Any emergent relationships will be explored through population PK/PD modeling.

The relationship between exposure to BAN2401 and most frequent AEs will also be explored.

PHARMACOGENOMIC/PHARMACOGENETIC ANALYSES

APOE4 genotypes or other important genomic/genetic findings will be used in the statistical analysis to determine the effects on treatment response and safety.

Exploratory PG and biomarker analyses may be performed and reported separately. Details of these analyses may be described in a separate analysis plan. (revised per Amendment 01)

9.7.1.8 Safety Analyses

Evaluations of safety will be performed on the Safety Analysis Set. The incidence of AEs (including changes from baseline in physical examination), out-of-normal-range laboratory safety test variables, abnormal ECG findings, anti-BAN2401 antibody titers, and out-of-range vital signs, suicidality (C-SSRS), along with change from baseline in laboratory safety test variables, ECGs, safety MRI, and vital sign measurements, will be summarized by treatment group using descriptive statistics. The safety analysis will be also be summarized by the following safety subgroups: age (≤ 65 years, > 65 years), sex (male, female), race (white, black, Asian, other), *APOE4* status, and clinical subgroup (MCI due to AD – intermediate likelihood or mild Alzheimer’s disease dementia). (revised per Amendment 07)

EXTENT OF EXPOSURE

Extent of exposure to study drug will be summarized as cumulative extent of exposure from Day 1 to Week 6 initially, and at 3 months intervals thereafter. The number and percent of subjects will be presented by treatment group. Duration of exposure will be summarized using descriptive statistics and by duration categories; Day 1 to 6 weeks, 6 weeks to 3 months, and 3-month intervals thereafter. The number and percent of subjects will be presented by each duration category and treatment group.

ADVERSE EVENTS

The AE verbatim descriptions (investigator terms from the eCRF) will be classified into standardized medical terminology using the Medical Dictionary for Regulatory Activities (MedDRA). Adverse events will be coded to the MedDRA (Version 15.0 or higher) lower level term (LLT) closest to the verbatim term. The linked MedDRA preferred term (PT) and primary system organ class (SOC) will also be captured in the database.

A treatment-emergent AE (TEAE) is defined as an AE that emerged during treatment or any time prior to the last study visit following the last dose of study drug, having been absent at pretreatment (Baseline) or:

- Reemerged during treatment, having been present at pretreatment (Baseline) but stopped before treatment, or
- Worsened in severity during treatment relative to the pretreatment state, when the AE was continuous.

Treatment-emergent AEs (TEAEs) and AEs will be followed for the entire duration of the study. Only those AEs that are treatment emergent will be included in summary tables. All AEs, treatment emergent or otherwise, will be presented in subject data listings.

TEAEs will be summarized by treatment group on the Safety Analysis Set. The incidence of TEAEs will be reported as the number (percentage) of subjects with TEAEs by SOC and PT. A subject will be counted only once within a SOC and PT, even if the subject experienced more than 1 TEAE within a specific SOC and PT. The number (percentage) of subjects with TEAEs will also be summarized by maximum severity (mild, moderate, or severe). The number (percentage) of subjects with TEAEs will also be summarized by relationship to study drug (possibly related, probably related, and not related).

Adverse events will be summarized by the following subgroups: age (≤ 65 years, > 65 years), sex (male, female), race (white, black, other), clinical subgroup (MCI due to AD – intermediate likelihood and mild Alzheimer’s disease dementia), the presence or absence of ongoing AD treatment (ie, AChEIs or memantine or both), and *APOE4* genotype.

The number (percentage) of subjects with TEAEs leading to death will be summarized by MedDRA SOC and PT for each treatment group. A subject data listing of all AEs leading to death will be provided.

The number (percentage) of subjects with treatment-emergent SAEs will be summarized by MedDRA SOC and PT for each treatment. A subject data listing of all SAEs will be provided.

The number (percentage) of subjects with TEAEs leading to discontinuation from study drug will be summarized by MedDRA SOC and PT for each treatment. A subject data listing of all AEs leading to discontinuation from study drug will be provided.

ANTI-DRUG (BAN2401) ANTIBODIES

The number (percentage) of subjects with positive and negative ADA, ADA titer categories (>0, 5, 25, 125, etc.), and neutralizing antibodies by visit and treatment group will be summarized (revised per Amendment 08). In addition, the correlation between ADA titer and PK profile or the correlation between ADA titer and efficacy will be evaluated using descriptive statistics and summary plots.

LABORATORY VALUES

Laboratory results will be summarized using Système International (SI) units, as appropriate. For all quantitative parameters listed in [Section 9.5.1.5](#). Safety Assessments (Laboratory Measurements), the actual value and the change from baseline to each postbaseline visit and to the end of treatment (defined as the last on-treatment value) will be summarized by visit and treatment group using descriptive statistics. Qualitative parameters listed in [Section 9.5.1.5](#) will be summarized using frequencies (number and percentage of subjects), and changes from baseline to each postbaseline visit and to end of treatment will be reported using shift tables. Percentages will be based on the number of subjects with both nonmissing baseline and relevant post-baseline results.

Laboratory test results will be assigned a low/normal/high (LNH) classification according to whether the value was below (L), within (N), or above (H) the laboratory parameter's reference range. Within-treatment comparisons for each laboratory parameter will be based on 3-by-3 tables (shift tables) that compare the baseline LNH classification to the LNH classification at each postbaseline visit and at the end of treatment. Similar shift tables will be used to compare the baseline LNH classification to the LNH classification for the highest and lowest value during the treatment period.

The Sponsor's Grading for Laboratory Values ([Appendix 1](#)) presents the criteria that will be used to identify subjects with treatment-emergent markedly abnormal laboratory values (TEMAV). Except for phosphate, a TEMAV is defined as a post-baseline value with an increase from baseline to a grade of 2 or higher. For phosphate, a TEMAV is defined as a postbaseline value with an increase from baseline to a grade of 3 or higher. When displaying the incidence of TEMAVs, each subject will be counted once in the laboratory parameter high and in the laboratory parameter low categories, as applicable.

VITAL SIGNS

Descriptive statistics for vital signs parameters (diastolic and systolic blood pressure, pulse, respiration rate, temperature, weight and changes from baseline) will be presented by visit and treatment group.

ELECTROCARDIOGRAMS

(revised per Amendment 01)

Abnormal ECG findings will be presented as shifts from baseline (normal/abnormal clinically significant/abnormal not clinically significant) to postbaseline (normal/abnormal clinically significant/abnormal not clinically significant) visits. The number and percent of subjects will be presented.

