At the time of Amendment 11, the Core Study was completed. Preliminary data analysis indicated that the incidence of amyloid-related imaging abnormality edema/effusion (ARIA-E) was less than 10% for the highest BAN2401 dose groups (10 mg/kg biweekly and monthly) and less than 8% overall for subjects receiving treatment with any dose level of BAN2401. There were 5 cases of symptomatic ARIA-E in BAN2401 treatment groups (all developed ARIA-E within the first 12 weeks of treatment): 1 severe ARIA-E on magnetic resonance imaging (MRI) at 2.5 mg/kg biweekly, reported as a non-serious AE; 1 mild ARIA-E on MRI at 10 mg/kg monthly, reported as a serious adverse event (SAE); 1 moderate ARIA-E on MRI at 10 mg/kg biweekly, reported as an SAE; and 2 severe ARIA-E on MRI at 10 mg/kg biweekly, both reported as SAEs. The breakdown of ARIA-E cases by ApoE4 status is provided in [Table 2](#), with the incidence being higher in ApoE4 carriers (<15% at top dose) than non-carriers (8% at top dose). (revised per Amendment 11)

Table 2 Summary of Treatment-Emergent ARIA-E by ApoE4 Status (Safety Analysis Set) (revised per Amendment 11)

Category	Placebo (N=245) n (%)	BAN2401							
		2.5 mg/kg biweekly (N=52) n (%)	5 mg/kg monthly (N=51) n (%)	5 mg/kg biweekly (N=92) n (%)	10 mg/kg monthly (N=253) n (%)	10 mg/kg biweekly (N=161) n (%)	Total BAN2401 (N=609) n (%)		
		ARIA-E	2 (0.8)	1 (1.9)	1 (2.0)	3 (3.3)	25 (9.9)	16 (9.9)	46 (7.6)
		APOE4 positive	2/174 (1.1)	1/38 (2.6)	1/40 (2.5)	3/84 (3.6)	23 ^a /225 (10.2)	7/49 (14.3)	35/436 (8.0)
APOE4 negative	0/71	0/14	0/11	0/8	2/28 (7.1)	9/112 (8.0)	11/173 (6.4)		

APOE4 = apolipoprotein ε4 variant, ARIA-E = amyloid-related imaging abnormality edema/effusion, TEAE = treatment-emergent adverse event

a: One additional ApoE4 positive ARIA-E case was observed after 18 month treatment database lock and after treatment discontinuation; therefore, by definition was not treatment-emergent and is not counted in this table or TEAE description above

After 18 months of treatment in any BAN2401 dose group overall, there were few reported cases of ARIA-E (n=46/609, 7.6%). Most cases of ARIA-E (approximately 61%) occurred within the first 3 months of treatment, were mild to moderate in radiographic severity on MRI, were asymptomatic (92%), and typically resolved within 4 to 12 weeks. (revised per Amendment 11)

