9.1.2.2 Follow-Up Period

Subjects who are not eligible or who do not elect to participate in the Extension Phase Part A will be required to continue into the Follow-Up Period in the Core Study. (revised per Amendment 08) During the Follow-Up Period, a single visit will take place approximately 3 months after the last dose of study drug. At this visit, safety assessments will be conducted including vital signs, a routine physical examination, weight measurements, a single 12-lead ECG, clinical laboratory tests, blood for serum anti-BAN2401, a safety MRI, the C-SSRS, and review of concomitant medications and AEs. (revised per Amendment 01) Clinical tests will be administered consisting of the MMSE, the CDR, the ADAS-Cog, and the FAQ.

Subjects who discontinue the study or study drug early must comply with the Early Termination Visit (within 7 days after the last dose of study drug) and the Follow-Up Visit (3 months after the last dose of study drug). The 3-month Follow-Up Visit is not required for any subject who transitions directly from the Extension Phase Part A or Part B (including the postmarketing section in Japan) of the study to commercial BAN2401 (revised per Amendments 18 and 19). Unscheduled visits for safety assessments may also be conducted. Subjects who discontinue due to *APOE* status are expected to return for an Early Termination Visit and 3-month Follow-Up Visit (ie, 3 months after the last dose of study drug). (revised per Amendment 06). In addition, all subjects who discontinue from study drug are expected to return after the Early Termination Visit for each scheduled visit when clinical assessments of efficacy are to be conducted per the Schedule of Procedures/Assessments ([Table 8](#)). (revised per Amendment 08) At these visits, clinical efficacy assessments (MMSE, CDR, ADAS-Cog, and FAQ) will be conducted and information on concomitant medications, AEs, and SAEs will be collected. Regularly scheduled clinical efficacy visits do not need to be attended if they fall within 8 days (visit window) after the Early Termination Visit or within ± 8 days of the 3-month Follow-Up Visit. Subjects who discontinue from study drug are considered on study as long as they return for their regularly scheduled clinical efficacy visits as outlined above. (revised per Amendment 01)

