All AEs observed during the study will be reported on the eCRF. All AEs, regardless of relationship to study drug or procedure, should be collected beginning from the time the subject signs the study ICF through the last visit (Visit 43, as shown in [Table 8](#) for the Core Study) (revised per Amendments 08, 09, and 11). SAEs will be collected up to 3 months after the last dose of study drug or through the last visit, whichever is longer. This includes those subjects who discontinue from study drug and who return for regularly scheduled visits where clinical assessments are conducted. (revised per Amendment 01)

For subjects who transition to commercial BAN2401 (including the postmarketing section in Japan), all AEs (including SAEs) will be followed until the end of the study, which will be the date of the last study evaluation prior to transitioning to commercial BAN2401 and at which time all assessments included in Week 261/Early Termination Visit (Part A) and Early Termination Visit (Part B) are to be performed according to the Schedule of Assessments of Part A and Part B, respectively are to be performed. (revised per Amendment 18 and 19)

Abnormal laboratory values should not be listed as separate AEs if they are considered to be part of the clinical syndrome that is being reported as an AE. Any laboratory abnormality considered to constitute an AE should be reported on the Adverse Event eCRF.

It is the responsibility of the investigator to review all laboratory findings in all subjects and determine if they constitute an AE. Medical and scientific judgment should be exercised in deciding whether an isolated laboratory abnormality should be classified as an AE.

Abnormal ECG (QTc) results, if not otherwise considered part of a clinical symptom that is being reported as an AE, should be considered an AE if (1) the QTc interval is >450 ms and there is an increase of >60 ms from baseline, or (2) the QTc interval is >500 ms. Any ECG abnormality that the investigator considers as an AE should be reported as such.

It is the responsibility of the investigator to review the results of the C-SSRS in all subjects and to determine if any of these results constitutes an AE. Medical and scientific judgment should be exercised in deciding whether or not an isolated suicidality rating scale response should be classified as an AE.

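### The TEAE rule runs to the last study visit for new events but stops with treatment for worsening, and Table 2 omits an ARIA-E case on grounds the rule does not contain

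*Protocol*

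**What the plan says.** Section 9.7.1.8 defines a TEAE in three limbs. An event absent at baseline counts if it "emerged during treatment or any time prior to the last study visit following the last dose of study drug". An event that was present before treatment and had stopped counts only if it returns during treatment. The third limb reads "Worsened in severity during treatment relative to the pretreatment state, when the AE was continuous". The section puts only treatment-emergent events into the summary tables and sends all other events to listings.

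The off-drug period in the first limb is real follow-up. Section 9.5.1.5 says AEs "should be collected beginning from the time the subject signs the study ICF through the last visit", which is Visit 43 in the Core Study. Section 9.1.2.2 says that "a single visit will take place approximately 3 months after the last dose of study drug", and a safety MRI is among its assessments.

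Section 7.1.2.3 reports, from a preliminary analysis, that ARIA-E incidence was "less than 10% for the highest BAN2401 dose groups (10 mg/kg biweekly and monthly") and below 8% across all BAN2401 doses. Table 2 gives the counts. Footnote a is attached to the APOE4-positive cell of the 10 mg/kg monthly arm. It says that one more case was "observed after 18 month treatment database lock and after treatment discontinuation; therefore, by definition was not treatment-emergent" and so is not in the table. The text also states "There were 5 cases of symptomatic ARIA-E in BAN2401 treatment groups" and puts the asymptomatic share of ARIA-E at 92%.

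**The concern.** There are three problems of different weight.

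- **Unequal end dates.** A new event after the last dose enters the safety tables. A continuing event that worsens in the same weeks, or an old one that returns, does not. Safety is a primary objective of the Core Study and the primary endpoint of Extension Parts A and B. Both Extension parts are to be analysed in the same way as the Core Study, and Appendix 4 refers back to 9.7.1.8 for Part A. The gap therefore carries forward into analyses still to be done.
- **A definition that is not in the protocol.** The footnote presents the exclusion as following from the meaning of treatment-emergent. Under 9.7.1.8, onset after stopping drug does not disqualify an event, and a database lock is a data cut-off, not part of the definition.
- **A percentage that does not match its counts.** The 92% cannot be obtained from the figures printed beside it.

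What is at stake is which off-drug findings reach the tables, and whether the published ARIA-E summary can be relied on as it stands.

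**Working it through.** **1. The three limbs side by side (section 9.7.1.8)**

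| Limb | Counts during treatment | Counts after last dose, up to last study visit |
|---|---|---|
| New event | yes | yes |
| Re-emergence | yes | no |
| Worsening of a continuing event | yes | no |

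**2. The footnote's grounds against the rule**

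| Ground in footnote a | Exclusion ground in 9.7.1.8? |
|---|---|
| After the 18-month database lock | no; the rule has no data cut-off |
| After treatment discontinuation | no; the first limb includes this period |
| After the subject's last study visit | would exclude the case, but the footnote does not claim it |

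**3. Table 2 as printed, incidence = cases / subjects**

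The rows add up: 1 + 1 + 3 + 25 + 16 = 46 cases and 52 + 51 + 92 + 253 + 161 = 609 subjects. In the monthly arm, 23 + 2 = 25 and 225 + 28 = 253. The printed percentages reproduce. Pooling the two 10 mg/kg arms gives (25 + 16)/(253 + 161) = 41/414.

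**4. With the excluded case counted**

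This adds one case to the arm and stratum that carry the footnote marker. It assumes a subject not already counted and unchanged denominators.

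| Group | As printed | With the case |
|---|---|---|
| 10 mg/kg monthly | 25/253 = 9.88% | 26/253 = 10.28% |
| Monthly, APOE4 positive | 23/225 = 10.22% | 24/225 = 10.67% |
| 10 mg/kg biweekly | 16/161 = 9.94% | unchanged |
| Both 10 mg/kg arms | 41/414 = 9.90% | 42/414 = 10.14% |
| All BAN2401 | 46/609 = 7.55% | 47/609 = 7.72% |

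Ten percent of 253 is 25.3, so one case takes the monthly arm across the line.

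**5. Asymptomatic share = (cases - symptomatic) / cases**

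- BAN2401 arms: (46 - 5)/46 = 41/46 = 89.1%, so the symptomatic share is 5/46 = 10.9%, against the 8% that 92% implies.
- Adding the 2 placebo cases, if both were asymptomatic: 43/48 = 89.6%.
- Adding the excluded case, if asymptomatic: 42/47 = 89.4%. Adding all three: 44/49 = 89.8%.
- No whole count out of 46 rounds to 92%: 42/46 = 91.3% and 43/46 = 93.5%.
- The neighbouring figure of about 61% within three months fits 28/46 = 60.9%, which supports 46 as the denominator.

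**The case against.** The strongest reply is that the excluded case has no date relative to the last study visit. The protocol allows extra safety visits more than 90 days after the final dose, so the timing cannot be inferred from the fact that ARIA-E is found on MRI. A reader might conclude that 9.7.1.8 requires the case to be counted and that the statement of less than 10% is false. The documents do not support that. They show only that the reason given is not the protocol's reason.

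The lock also matters. Table 2 reports a preliminary analysis of locked 18-month data, and a case seen later would be absent from it under any window. That is a legitimate cut-off, but it is not a matter of definition, which is how the footnote presents it.

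Table 2 is background and governs no later count, the sponsor disclosed the case beneath the table, and no protocol decision turns on 10%. All of that stands and limits the weight of the second problem. The SAP may define the window differently, but a different SAP definition would still conflict with 9.7.1.8 as written.

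Two further inferences should be resisted. A reader might think that extra microhemorrhages on a follow-up MRI would be lost as mere worsening. Section 9.5.1.5 makes new microhemorrhages adverse events in their own right, so they fit the first limb. A reader might also think that the case understates the risk at the Extension's biweekly dose. It belongs to the monthly arm, and the biweekly figures do not move.

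The unequal limbs and the 92% are not answered by any of this. Listings and the separate MRI summaries soften the first, but they do not put off-drug worsening into the TEAE tables.

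**Conclusion.** The point holds in a limited form. Section 9.7.1.8 has unequal end dates on its face, and no assumption is needed to see it. Its numerical effect cannot be sized from the protocol. The footnote's appeal to a definition contradicts 9.7.1.8, also on its face.

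The change in incidence is conditional on the case having arisen before that subject's last study visit, being in the arm that carries the marker, and not being counted already. Under those conditions the statement of less than 10% fails for the monthly arm by about 0.3 percentage points and for the pooled 10 mg/kg arms by about 0.1. It remains true for biweekly, and the statement of less than 8% overall also survives.

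The 92% is wrong against the text's own counts, by about 3 percentage points, whatever is decided about the excluded case.

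**What to change.** 1. In 9.7.1.8, use one end date, the last study visit after the last dose, for onset, re-emergence and worsening. Word it so that a finding made at that visit is clearly included. Apply the same rule to the safety analyses of Extension Parts A and B.
2. Establish the date of the excluded case against that subject's last study visit. If it falls inside the window, count it and restate Table 2 and the text: 26/253 (10.3%), 24/225 (10.7%) and 47/609 (7.7%), with the actual figures in place of the less-than-10% sentence. Otherwise, replace the appeal to a definition with the true reason, either the data cut-off or onset after the last visit. If a data cut-off is the reason, say that the table is as of that cut-off.
3. Change 92% to 89% (41/46).

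The cost is protocol wording, matching SAP wording and at most one table re-run. One reported incidence may become slightly less favourable.
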